## Version History

Date (dd-mm-yyyy)	Version	Reason for the update
22-02-2024	1.0	First draft of SAP based on original trial protocol

## **ABSTRACT**

### **Background**

This a priori statistical analysis Plan describes the analyses for INORDINATE

### **Methods:**

INORDINATE (Inhaled Nitric Oxide ReDuce postoperative pulmoNary complications in patiEnts with recent COVID-19 infection) aims to determine whether the inhalation of high-concentration nitric oxide (NO) during surgery will decrease postoperative pulmonary complications in surgical patients with recent (within 7 weeks) SARS-CoV2 infection history. The study is a single center parallel, two-arm, superior, randomized clinical trial. In total, 660 adult patients with recent SARS-CoV-2 infection scheduled for surgery under general anesthesia and mechanical ventilation will be included. After anesthesia induction, patients will be mechanically ventilated and randomly assigned to inhaled 80 ppm NO or placebo until the end of mechanical ventilation or leave the operation room(OR), whichever comes first. The primary outcome is a composite measure of postoperative pulmonary complications (PPCs), recorded as a composite endpoint within the first seven postoperative days. Secondary endpoints include postoperative 30-day all-cause mortality, severity of PPCs scaled by Clavien-Dindo classification, unplanned ICU admission, postoperative length of hospital stay, thrombotic events (including deep venous thrombosis and pulmonary embolism); and postoperative

comprehensive complication index (CCI). The main analyses will focus on the primary and secondary outcomes for recent infected patients undergoing surgery with mechanical ventilation. The analysis will use an intention-to-treat approach to compare treatment arms.

**Conclusions:**

This documents provides a detailed statistical analysis plan for INORDINATE.

**Funding:**

The trial is funded by the National Natural Science Foundation of China (81970448), the university and hospital foundation for patient outcome improvement (2021LC2202, XJZT21L17, XJZT23XG22 and XJZT24LZ04)

**Trial registration:**

ClinicalTrials.gov identifier: NCT05721144. Registered on February, 07, 2023.

**Keywords:**

COVID-19, Nitric Oxide, Surgery, Prognosis, Inhalation, Perioperative Management, Pulmonary complications, Statistical analysis plan

## **Background**

It has been reported that a history of SARS-CoV-2 infection is associated with a transiently elevated risk of postoperative complications [1–3]. An updated recommendation suggested postponing surgery for at least seven weeks following SARS-CoV-2 infection, thereby reducing the risk of postoperative complications and 30-day mortality to baseline levels (similar to those without a history of SARS-CoV-2 infection) [4–6]. Postoperative pulmonary complications (PPCs) were the most common and frequent complications in patients with a history of COVID-19 infection [2, 7]. Even mild PPCs is associated with increased incidence of postoperative short-term mortality, ICU admission, and prolonged length of ICU and/or hospital stays[15]. Various strategies have been proposed to prevent or mitigate PPCs but with limited efficacy.

In recent years, there has been growing interest in the use of inhaled nitric oxide (iNO) as a potential prophylactic or therapeutic intervention for PPCs. iNO, a selective pulmonary vasodilator, has demonstrated its ability to improve oxygenation, reduce pulmonary hypertension [8], and modulate inflammation in various clinical settings, including pulmonary hypertension, acute lung injury, and ARDS [9-12]. Moreover, iNO has been shown to have a favourable safety profile, with few serious adverse events reported [13]. For patients underwent cardiac surgeries, iNO has been shown to dilate pulmonary blood vessels [14],

reduce pulmonary arterial pressure and lower pulmonary vascular resistance [15-20], and significantly improve oxygenation and patients prognosis [21, 22]. Particularly in patients undergoing aortic dissection surgeries, low-dosed iNO was shown to improve oxygenation, thereby reducing the duration of mechanical ventilation and ICU stay [23]. Additional benefits include a reduction in postoperative complications related to inflammatory responses among patients undergoing knee replacement surgery [24].

The guidelines pertaining to the management of critically ill adults with Coronavirus Disease 2019 [25] recommended administration of inhaled oxide as a rescue therapy for COVID-19 patients experiencing refractory hypoxemia [26]. Studies have proposed NO inhalation as an effective strategy for COVID-19 treatment [27], as SARS-CoV-2 modulates endogenous NO levels and availability upon entering host cells. It was demonstrated that NO can reduce SARS-CoV-2 viral load by 95% within 24 hours and over 99% within 72 hours [28]. Despite its theoretical plausibility and potential, the clinical evidence supporting the efficacy of NO in treating COVID-19-related pulmonary complications has primarily originated from observational studies [29, 30] or small trials [31], yielding inconsistent reported results. Recently, a phase II study demonstrated an improvement of  $\text{PaO}_2/\text{FIO}_2$  with high-dose NO (at 80ppm) at 48 hours compared with usual care in adults with acute hypoxic respiratory failure due to COVID-19 [32]. Although the clinically important hard outcomes did not differ, the exploratory results suggested that

inhaled NO leads to a steeper reduction in plasma viral load. In addition, at 80 ppm (relatively high dose), iNO was safe and well-tolerated.

The rationale for using iNO in treating surgical patients with COVID-19 is well established and lies in several key mechanisms. There are however very limited study exploring whether inhaled NO can improve postoperative lung function, especially in non-cardiac surgeries. Furthermore, no randomised controlled trial is available evaluating iNO in surgical patients with a history of recent SARS-CoV-2 infection [33].

INORDINATE is a single-center, randomized placebo controlled trial that aims to determine if intraoperative inhalation of 80 ppm NO will reduce the postoperative pulmonary complications in surgical patients with recent (within 7 weeks) SARS-CoV-2 infection.

The trial commenced in February 17, 2023 and the estimated timeline for completion of patient accrual was 12 months. Duration of participation for each patient is 30 days (last follow-up). The total study duration is estimated to be approximately 13 months. This statistical analysis plan details the planned analyses for INORDINATE to facilitate the transparency of data analyses. The trial protocol has previously been published [34].

## **STUDY OVERVIEW**

### **Ethics and Study Design**

Single centre, randomized superiority trial of inhaled nitric oxide during intraoperative mechanical ventilation compared to standard care with placebo nitrogen inhalation in a tertiary teaching hospital. The study protocol has been approved by the institutional review board (IRB) at Xijing Hospital (KY20232058-F1) and has been registered on ClinicalTrials.gov as INORDINATE trial with the identifier NCT05721144. The informed consent will be collected by investigators for all patients before inclusion in the trial. No interim analyses is planned.

## **Study population**

Adult participants (18 years of age or older) recently infected with SARS-CoV-2 within 7 weeks and scheduled for surgery under general anaesthesia with mechanical ventilation are potentially eligible for INORDINATE.

Table 1. Eligibility Criteria

---

Inclusion	

1. Patients who are <math>\geq</math> 18 years old;

2. Patients who are diagnosed COVID-19 via RT-PCR, rapid antigen or clinical symptoms verified by trained professionals;

3. Surgery should have taken place within 7 weeks of diagnostics of COVID-19;

4. Patients should have understood and signed the informed consent.

-----------	--

1. The healthcare professionals, including surgeons, anesthesiologists, and other personnel responsible for the patient's treatment, or the investigators, have chosen to abstain from participating in the study. Their decision is grounded in the belief that the patient may not derive significant benefits from inhaled nitric oxide (iNO)
2. ASA  $\geq 4$  or life expectancy  $< 24h$ ;
3. Females during pregnancy or lactation;
4. Patients with severe liver diseases (defined as Child Pugh score  $\geq 12$ );
5. Patients with severe respiratory failure, requiring mechanical ventilation or ECMO support before surgery;
6. Patients with severe kidney dysfunction (eGFR  $\leq 30$  ml/min/1.73m^2) or requiring any of ordinary renal replacement therapy, hemodialysis or peritoneal dialysis;
7. Patients who have been participating in a different clinical trial within a month.

---

## **Randomization and Masking**

Eligible participants will be randomly allocated at 1:1 ratio to either NO inhalation or placebo. The randomization process will utilize permuted-block randomisation, with stratification based on the predicted risks of PPCs using the Assess Respiratory Risk in Surgical Patients in Catalonia (ARISCAT) index (< 45 [low and medium risk],  $\geq 45$  [high risk]), as well as the time interval from infection to surgery ( $\leq 10d$ , 11-28d, 29-49d). Random blocks of 4 or 6 will

be used for randomization. The allocation will be concealed by a web-based system that was accessed no earlier than the morning of the surgery.

## **Intervention**

All participants will receive perioperative management based on our institutional standard practice, which includes various components such as preoperative evaluation and preparation, general anaesthesia with or without neuraxial anaesthesia and/or nerve blocks, mechanical ventilation, inotropic drugs and vasopressors, postoperative sedation and analgesia, diuretics, intravenous fluids, antibiotics and invasive monitoring. This management regimen will encompass a range of interventions and monitoring, including but not limited to non-invasive or invasive arterial pressure, electrocardiogram, central venous pressure, cardiac output, pulse oximetry, temperature, urine output, arterial blood gases, coagulation monitoring, and frequent routine laboratory examinations. No additional interventions or laboratory tests beyond the standard perioperative management will be conducted on participants. All perioperative management will be at the discretion of the treating anesthesiologist and in accordance with existing protocols for patients undergoing surgery and equal for both groups. Predicted body weight will be calculated as  $50 + 0.91 * (\text{height [cm]} - 152.4)$  for male and  $45.5 + 0.91 * (\text{height [cm]} - 152.4)$  for female. Patients will be randomized into one of the following interventions (Figure 1):

[figure not shown]
*Inhalation of NO:*

After randomization, patients assigned to NO group will receive NO inhalation at a concentration of 80 parts per million (ppm) through the respiratory circuit of a mechanical ventilator. The intervention will commence immediately after tracheal intubation and will persist until either extubation or the patient exits the operation room, whichever happens first.

*Placebo group:*

After randomization, patients assigned to placebo group will receive standard care and inhalation with the NO vehicle gas, aka nitrogen through the respiratory circuit of a mechanical ventilator. The intervention will commence immediately after tracheal intubation and will persist until either extubation or the patient exits the operation room, whichever happens first.

For the intervention details, please refer to the published protocol [34].

**Figure 1. Flowchart**

## Data collection

A prespecified and designed case report form (CRF) will be used for data collection. All data collected for the trial will be entered into the REDCap application by trained research staff from the clinical chart source data. Access to the data will be restricted and granted by the principal investigator (PI) to authorized investigators within the study team. To ensure the quality

and integrity of collected data, various measures are implemented. After completing the data collection (Table 2), the database will be locked and only the PI ([name]) and the statistician ([name] and [name]) responsible for the analyses will have access to it.

## **STUDY OUTCOMES**

### **Primary Endpoint**

The primary endpoint is a composite measure of postoperative pulmonary complications (PPCs) occurring within the first seven days after surgery. Components include respiratory infection, respiratory failure, pleural effusion, atelectasis, pneumothorax, bronchospasm, aspiration pneumonitis, and pneumonia ([detailed definition please refer to the published protocol \[34\]](#)).

### **Secondary Endpoints**

Secondary endpoints include postoperative 30-day all-cause mortality, severity of PPCs scaled by Clavien-Dindo classification, unplanned ICU admission, postoperative length of hospital stay, thrombotic events (including deep venous thrombosis and pulmonary embolism); and postoperative comprehensive complication index (CCI). Details on definition can be found in [the published study protocol \[34\]](#). Other measurements are non-pulmonary complications including stroke, cardiac infarction, ventricular dysfunction, delirium, acute kidney injury, surgical revision for bleeding,

hypotension/hypertension, arrhythmia, hyper-responsiveness.

## STATISTICAL ANALYSIS PLAN

### Scope of the Analysis plan

This Statistical Analysis Plan (SAP) presents the analyses for the INORDINATE trial. The final manuscript will include follow-up data until leaving hospital for the trial and analyses will follow this SAP strictly.

### Sample Size Consideration

The sample size for this study has been calculated based on the incidence of postoperative pulmonary complications of incidence of PPCs is reported to be approximately 20% for all surgical populations [62, 63] and increase up to 39.5% after COVID-19 infections[5]. The study assumes a 30% PPC incidence in the control group. We anticipate a 30% relative reduction (from 30% to 20%) in PPCs incidence for the iNO group. At 5% significance level and on consideration of 10% dropouts, the sample size needed to achieve 80% power is thus calculated to be 660 (330 per group) using a

two-sided Chi-squared test with continuity correction.

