## Datasets for analyses

All statistical analyses will be conducted on an intention-to-treat basis, with patients analyses according to their assigned treatment arms (Figure 1). No or minimal losses to follow-up for the primary and secondary outcomes are anticipated. Complete – case analysis will be carried out for all the outcomes. However, if more than 5% of missing data were found for the primary outcome, a sensitivity analysis using multiple imputations and estimating – equation methods will be carried out.

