## **General Approach**

INORDINATE is designed to detect whether intraoperative administration of up

to 80 ppm NO can reduce PPCs from 30% to 20% in participants undergoing surgical procedures under general anaesthesia who have been infected with SARS-CoV-2 within 7 weeks. Hypothesis tests will be two – sided with a significance level of 0.05. Strength of evidence (e.g., confidence intervals around estimates) will be provided. Data will be screened for integrity prior to full analysis.

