## **Missing and outlier Data**

We anticipate no missing values in the primary outcome and very low missing values in other variables if any. The demographics and chronic medical history will be filled on site, intraoperative data will be monitored and recorded in the operating rooms, and the follow-ups until discharge of hospital or deaths can be traced back in the electronic health records. If patients are lost during the 30-day follow-ups, no imputation will be conducted for outcomes. Data missing at baseline will be reported as such. In case where low missing rate (<5%) occurred with no trace-backs available, multiple imputation will be performed as a sensitivity analysis.

Outliers will be subject to a confirmation request to the investigators. In

case of confirmation, their value will not be modified, and will be taken into account as it is during the analysis.

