## **Primary Analysis**

The effects of inhaled NO on incidence of PPCs will be reported as number and percentages and estimated with risk ratio and 95% confidence intervals calculated with Wald's likelihood ratio approximation test and with Chi-squared or Fisher's exact test for hypothesis testing. The unadjusted analysis will estimate risk ratios with 95% confidence intervals by two-by-two table with the use of log-Normal approximation. In addition, the effect size will be expressed as risk differences (95% confidence intervals) with the number needed to treat as the reciprocal of the risk difference, rounded to the nearest integer. This will further be analysed as the generalised linear models (GLM) under binomial family with either log or logit link where appropriate. Odds ratios or relative risks together with 95% confidence intervals will be reported. Further adjustment on stratification variables such as ARISCAT index and time interval from infection to surgery will be made. The point estimates with 95% confidence intervals will be reported.

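### With the stated test and 10% dropout, 660 patients give about 78% power rather than 80%, and 30% to 20% is a 33% relative reduction rather than 30%

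*SAP*

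**What the plan says.** All the inputs are in the SAP, under Sample Size Consideration. The control rate is 30%, and the effect is given as "We anticipate a 30% relative reduction (from 30% to 20"%). The error rate and loss allowance are introduced with "At 5% significance level and on consideration of 10% dropouts". The conclusion is that "on consideration of 10% dropouts, the sample size needed to achieve 80% power is thus calculated to be 660 (330 per group"), and the method is named as a "two-sided Chi-squared test with continuity correction".

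Four other sections bear on the point:
- General Approach repeats the design effect: nitric oxide "can reduce PPCs from 30% to 20% in participants undergoing" surgery.
- Datasets for analyses says "No or minimal losses to follow-up for the primary and secondary outcomes are anticipated".
- Missing and outlier Data says "We anticipate no missing values in the primary outcome".
- Primary Analysis names chi-squared or Fisher's "exact test for hypothesis testing" and does not say whether the chi-squared test is corrected.

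Allocation is 1:1 (Randomization and Masking), and no interim analysis is planned (Ethics and Study Design). Nothing else enters the calculation.

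**The concern.** The paragraph names its test, rates, error levels and loss allowance, so a reader should be able to recover 660 from it. Using the continuity correction, one cannot. The stated 80% power is therefore not what the stated design delivers if the allowed losses occur.

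Separately, the relative reduction does not match the two rates printed beside it. A true 30% relative reduction would take 30% to 21%, a smaller effect for which 660 patients would be clearly too few. The label therefore describes an effect the trial is not sized for.

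What is at stake is the accuracy of a statement that will be reported with the trial and checked by readers. The validity of the primary comparison is not affected.

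**Working it through.** **Inputs (Sample Size Consideration):** p1 = 0.30, p2 = 0.20, mean p̄ = 0.25, difference d = 0.10, two-sided α = 0.05 (z = 1.960), power 80% (z = 0.842), 10% dropout, 1:1 allocation.

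**1. Uncorrected size per arm**

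- Pooled variance: n = [1.960·√(2·0.25·0.75) + 0.842·√(0.30·0.70 + 0.20·0.80)]² / 0.10² = (1.2002 + 0.5119)² / 0.01 = 293.2.
- Unpooled variance: n = (1.960 + 0.842)²·0.37 / 0.01 = 290.4.

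**2. With the continuity correction**

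n_c = (n/4)·[1 + √(1 + 4/(n·d))]²

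- Pooled: (293.2/4)·(1 + 1.0660)² = 312.8, so 313 per arm.
- Unpooled: (290.4/4)·(1 + 1.0666)² = 310.1, so 311 per arm.

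**3. Allowing for 10% dropout**

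| Variance | Inflation | Per arm | Total |
|---|---|---|---|
| Pooled | ÷ 0.9 | 347.6 → 348 | 696 |
| Pooled | × 1.1 | 344.1 → 345 | 690 |
| Unpooled | ÷ 0.9 | 344.5 → 345 | 690 |
| Unpooled | × 1.1 | 341.1 → 342 | 684 |

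No version gives 660. The gap runs from 24/660 = 3.6% to 36/660 = 5.5%.

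**4. Attempts to reproduce 660.** Two nearby sets of inputs come close, each changing one stated input:

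- Dropping the correction and keeping 10% loss: 294/0.9 = 326.7, so 327 per arm and 654 in total.
- Keeping the correction and using 5% loss: 313/0.95 = 329.5, so 330 per arm and exactly 660.

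The document cannot show which of these, if either, was used.

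**5. Power that 660 delivers.** After 10% loss, 330 × 0.9 = 297 per arm. By formula with the correction, z = (0.10 − 1/297 − 1.960·0.03553)/0.03530 = 0.765, which is 77.8% power. The exact column sums binomial probabilities over all tables that the test rejects.

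| Evaluable per arm | Meaning | Corrected, formula | Corrected, exact |
|---|---|---|---|
| 297 | 10% loss | 77.8% | 77.9% |
| 300 | 330/1.1 | 78.2% | 78.4% |
| 313 | about 5% loss | 80.0% | 80.1% |
| 330 | no loss | 82.2% | 82.4% |

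For comparison, the uncorrected test at 297 per arm has 80.5% power by formula and 80.8% exact.

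**6. Relative reduction.** (0.30 − 0.20)/0.30 = 33.3%. A 30% relative reduction would be 0.30 × 0.70 = 21%. At 297 per arm that effect would have 67.9% power by formula with the correction and 71.2% without.

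**The case against.** The best defence is that this hardly matters. The shortfall is about two points and appears only if the full 10% is lost. The SAP expects almost no loss: patients are randomised after induction of anaesthesia, and the primary endpoint is read within seven days. With complete data, corrected power is 82.4%, and it stays at about 80% with up to about 5% loss. The SAP is dated 22 February 2024, a year after the trial began and at the end of the planned 12 months of accrual, so the figure no longer drives recruitment. On the label, both rates are printed beside it and repeated in General Approach, so no reader would mistake the design effect.

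Most of that stands, and it is why no extra patients are asked for. It does not rescue the statement itself, which claims 80% power with 10% dropout already allowed for.

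A second objection is that the source of the mismatch should not be prejudged. That is right. The corrected test with 5% loss gives 660 exactly, so the dropout figure could be the slip just as the mention of a correction could be. Dropping the correction merely to recover 80% would not be a neutral edit either. At a common rate of 25% and 297 per arm, exact type I error is 0.040 with the correction and 0.050 without, so the choice can affect significance near the threshold. Restating the power for the test as named is correct whichever input was wrong.

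**Conclusion.** The concern holds. Under the SAP's own inputs, 660 randomised patients with 10% loss give 77.9% exact power (77.8% by formula), not 80%. The stated method would need 684 to 696. The relative reduction is 33.3%, not 30%.

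The power result assumes the two rates as stated, equal arms, and the continuity-corrected test as named. The shortfall disappears at about 5% loss or less. The relative reduction error is one of labelling, since the SAP gives 30% to 20% as the design effect in two places and nothing suggests that 21% was intended. Neither error biases the treatment estimate or raises the type I error rate.

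**What to change.** 1. Look up the original calculation to see whether the correction, the dropout rate or the total was misreported.
2. In Sample Size Consideration, keep 660, the named test and the 10% allowance. Replace the 80% claim with power of about 78% if 10% are lost and about 82% with no loss. The figure of about 80% at 5% loss can be added. If step 1 shows that another input was used, report that openly alongside these figures.
3. Replace the 30% relative reduction with a 33% relative (10 percentage point absolute) reduction.

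Whether the primary chi-squared test is corrected should also be stated in Primary Analysis. That choice should be made on its merits and before unblinding, not to recover the 80%.

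The cost is SAP wording only. There are no extra patients and no design change; the stated power at 10% loss falls by about two points.
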